The specific aims of this pilot study are: **Aim 1)** *To identify whether no prep ready to eat meals (intervention) or ingredient bundles (control) have higher client acceptability, liking, satisfaction, and perceived diet quality ratings.* **Hypothesis:** No prep ready to eat meals will have higher client acceptability, liking, satisfaction, and perceived diet quality scores than ingredient bundles. **Rationale:** Previous research has shown that acceptance, liking, satisfaction, and perceived diet quality are important determinants of the foods people are willing to eat and the ultimate success of diet-related interventions¹². Aim 1 will establish which strategy is most acceptable and desirable for food pantry clients to inform the development of a future randomized-controlled trial that will aim to test which strategy is most effective at improving objective dietary quality and reducing health-related risk factors. **Aim 2)** *To identify whether no prep ready to eat meals (intervention) or ingredient bundles (control) have higher feasibility ratings with food pantry staff.* **Hypothesis:** No prep ready to eat meals will have higher feasibility ratings than ingredient bundles among pantry staff. **Rationale:** It's unclear how much staff time and pantry resources are needed to put together an ingredient bundle from a recipe or store no prep ready to eat meals in appropriate refrigeration units. This pilot study will determine the resources needed to carry out each program and determine which is preferable and feasible for the pantry staff that would be asked to carry out either model given that staff buy-in is a key component to intervention success¹³.

2. Background.

- Describe past experimental and/or clinical findings leading to the formulation of your study.
- For research involving investigational drugs, describe the previously conducted animal and human studies.
- For research that involves FDA approved drugs or devices, describe the FDA approved uses of this drug/device in relation to your protocol.
- Attach a copy of the approved labeling as a product package insert or from the Physician's Desk Reference.

You may reference sponsor's full protocol or grant application (section number and/or title) or if none, ensure background includes references.

Please respond to all components of this item, or clearly indicate which components are not applicable.

a. Background

Reviews conducted in 2019 and 2022 have highlighted the urgent need for disease prevention strategies within the charitable food system, given the lack of evidence-based interventions. The most commonly reported interventions provide nutrition education, referrals to a social worker or health care provider, and/or behavioral economic approaches that "nudge" clients to select healthier options in client choice pantries^{22,23}. Some of these strategies have been effective at increasing food security and improving client selection of healthier food items at one point in time, however, it is a small literature base, few studies have been designed for long-term sustainability in partnership with pantry clients and staff, and most haven't measured changes in food intake.

One promising nutrition intervention is ingredient bundling, which pairs fruits, vegetables, whole grains, and lean proteins with a recipe that instructs participants on how to cook the meal. Ingredient bundles have been shown to increase ones perceived value of goods²⁴ and are hypothesized to reduce some of the search and planning time associated with making healthier food choices²⁵. Bundles were reported as a preferred nudging strategy by pantry clients in a formative research study⁵ and were found to increase selection of kale and whole grains when compared to recipe tasting and "treatment as usual" control groups in a between-subjects experiment in Connecticut⁹. However, in a study of Supplemental Nutrition Assistance Program (SNAP) shoppers, meal bundles were ineffective at improving grocery purchases²⁵ and no additional studies promoting ingredient bundles have been conducted in food pantries to determine if the Stein et al. findings are replicable.

While there are clear advantages of ingredient bundling, there are some disadvantages. There is staff time associated with identifying recipes and bundling ingredients from the available food donations or procurements and there is the added time and food preparation burden for clients. Furthermore, previous research has highlighted that people experiencing food insecurity may not have as much kitchen space or equipment as people who are food secure¹⁰. Among a sample of 211 Crossroads clients specifically, 55% did not have a mixing bowl, 54% reported not owning a casserole dish, and 23% did not

Form A

IRB # STU 2022-0809

have cutting knives or a blender²⁶, these are kitchen tools frequently recommended for healthier meal preparation strategies and required to prepare many recipes, such as stir fries, smoothies, and casseroles.

No prep ready-to-eat meals alleviate the time and food preparation constraints faced by people experiencing food insecurity and provide the opportunity to encourage more nutritious food consumption in a potentially preferable package. While market research and consumer scientists have identified no prep ready-to-eat meals as a burgeoning food retail avenue²⁶, these meals have not been empirically tested as a strategy for improving food security, dietary quality, and health outcomes among clients in a food pantry setting. Given the novelty of this idea, formative research is needed to confirm the intervention is desirable to food pantry clients and feasible for food pantry personnel to carry out.

b. Current practice

[figure not shown]
Currently, food pantry clients at Crossroads receive food in one of three ways:

- 1) Emergency box filled with food provisions filled by pantry staff – the number of pounds received is dependent on the household size and age of household members, the pantry client does not get to choose the food they receive
- 2) With an appointment, clients walkthrough the pantry and select food off shelves and from inside refrigeration units based on a point system – points are distributed based on household size and age of household members and the pantry inventory, the pantry client chooses the food they receive
- 3) With an appointment, clients select food using a web-based application that displays live inventory. Clients select food using the application based on the same in-house point system, the pantry client chooses the food they receive

3. Study Design.

Describe the study design (e.g., single/double blind, parallel, crossover, etc.) Consider inserting a scheme to visually present the study design.

Figure 3. Proposed study design

To test the first hypothesis, I will use a randomized repeated measures between-subjects design with half of the participants randomized to receive 14-days of no prep ready-to-eat meals (intervention, n=35) and half of the participants randomized to receive 14-days of ingredient bundles (control, n=35) (Figure 3).

To test the second hypothesis, I will use a mixed-methods approach with food pantry staff (N=10), including questionnaires with fixed and open-ended items on feasibility and satisfaction of each distribution strategy followed by 30-minute semi-structured 1-1 interviews conducted by UT Southwestern study staff.

4. Research Plan / Description of the Research Methods:

4.a. Provide a comprehensive narrative describing the research methods.

- 1) Provide the **order in which tests/procedures will be performed**,
- 2) Provide the **setting** for these events and a description of the **methods used to protect privacy** during the study.
- 3) Provide the **plan for data analysis** (include as applicable the **sample size calculation**)

Please respond to all components of this item, or clearly indicate which components are not applicable.

C.1.5 Intervention Methods

After completing consent forms, participants will be randomized to receive no prep ready-to-eat meals or ingredient bundles using random number generation. Participants will be unaware of their assignment until they are asked to select study meals, in which case it will be obvious because of the food items available to select. Participants will complete questionnaires and then select meals – they can select up to 2-meals, or the bundles needed to make 2-meals, for 14-days for themselves and 2 additional members of their household. Participants will elect to receive one week of meals after selection and come back to pick-up the second week of meals or they will take home all study meals at one time (participants choice). Participants will return at the end of the 2-week study period to complete the follow-up questionnaires and receive payment. A study timeline of intervention components and data collection is provided in **Table 1** to aid visualization of the study plan and timeline for **food pantry clients**.

Table 1. Study plan and timeline for food pantry clients.

Baseline appointment (Day 0)	Intervention (Day 1 - Day 14)	Follow-up appointment (Day 15)

 1. Informed consent 2. Randomization 3. Questionnaires (demographics, current pantry use, acceptability, satisfaction, liking, diet quality) 4. Selection of preferred no prep ready-to-eat meals OR ingredient bundles from the available study foods depending on study assignment 5. Follow-up appointment scheduled 	
 1. Participants and family members consume no prep ready-to-eat meals or ingredient bundles at-home for 14-days 2. Depending on the client's preference, reminder phone calls, texts, and/or emails are sent leading up to their follow-up appointment 	
 1. Questionnaires (demographics, current pantry use, acceptability, satisfaction, liking, diet quality) 2. Participant thank you and payment

C.1.5.1 No prep ready-to-eat meals

Roots Food Group provides nutrient-dense dietitian developed no prep ready-to-eat meals to many of the 14 million people on Medi-Cal in California through Aetna and HealthNet. The community-based 501c3 arm of Roots Food Group, Roots Food Foundation, provides the same meals and other resources to people living with blindness at no cost. Roots Food Foundation has agreed to donate and supply meals for this study.

Pantry clients will select study meals for up to 14-days' worth of meals for themselves and 2-members of their household using Crossroads online food selection platform (this platform is already built and is how clients currently select pantry foods). Roots Food Group produces over 70 meals. We have elected to study 14-days of meals to offer clients variety and determine which flavors are most desirable to clients. After ordering, meals will be retrieved from a refrigeration unit, boxed by pantry staff, and brought to the participant to take home. An example dinner is "Teriyaki Chicken with Roasted Potatoes and Broccoli", and an example breakfast is "Omelet with Peppers and Zucchini". Meals can be stored in a refrigerator or freezer and eaten immediately or after reheating depending on the meal and consumer preference. 94% and 86% of Crossroads clients reported owning a refrigerator and microwave respectively when previously surveyed²⁷ and microwaves are available in many community centers and gas stations for public use. This makes no prep ready-to-eat meals a potential solution to many of the challenges faced by Crossroads pantry clients and people experiencing food insecurity.

C.1.5.2 Ingredient bundles

Ingredient bundles will group individual meal ingredients (e.g., chicken, teriyaki, broccoli, potatoes) in a bag or box and pair those healthy food items with a recipe that instructs the client on how to make a healthier meal. Similar to the no prep ready-to-eat meal initiative, clients will select ingredient bundles for themselves and 2-members of their household using Crossroads online food selection platform. The no prep ready-to-eat meals chosen by the PI will be selected based on the ability to closely replicate the meal as an ingredient bundle using food pantry inventory. "Teriyaki Chicken with Roasted Potatoes and Broccoli" is an example of a Roots Food Group meal that will be available for clients to select as most of the required ingredients are purchased by or donated to Crossroads and typically available to clients. For this study, the study team will purchase groceries for this group. This is to ensure availability of study foods and to procure specific ingredients, such as spices and sauces (e.g., teriyaki), cooking oils, and fresh fruits and vegetables. Having costs associated with ingredient bundles also makes the expense burden associated with each strategy more equal, which helps confirm the feasibility and sustainability of either intervention going forward.

C.1.6 Measures**C.1.6.1 Pantry Client Measures**

At the baseline appointment participants will complete informed consent and a questionnaire that includes demographics, typical food pantry utilization, satisfaction, acceptability, liking, and perceived diet quality. Satisfaction items will be adapted from previously validated food pantry client satisfaction surveys (e.g., "How satisfied are you with the amount/variety/frequency of food that you and others in your household receive at this food pantry?")²⁸. Possible responses range from very satisfied and somewhat satisfied to somewhat dissatisfied and very dissatisfied. Liking of study foods will be measured by showing the name and picture of the meal or ingredient bundle and asking participants to respond to a hedonic 9-point bipolar scale with four measures of liking and four measures of dislike and a neutral "neither like nor dislike" item²⁹. Acceptability will be measured by showing the name and picture of the meal and asking the client whether they and/or members of their household ate the meal within the past 2-weeks and whether they would select the meal again if given the opportunity in the future³⁰. Perceived dietary quality will be measured using a single validated item that asks participants to rate their overall diet quality as "excellent," "very good," "good," "fair," or "poor"³¹. At the follow-up appointment, participants will complete the same liking and acceptability ratings, and a similar satisfaction questionnaire and perceived diet quality item, except wording will be slightly modified to "How satisfied were you with the amount of food that you and others in your household received at the food pantry **in the past 2-weeks?**" "How would you rate your dietary quality **over the past 2-weeks?**". These measures will allow us to determine between-group

Form A

IRB # STU 2022-0809

differences at baseline as well as within- and between-group changes in acceptability, satisfaction, liking, and diet-quality after consuming meals over time. These measures will also identify client's preferred meal flavors and frequency as well as the quantity desired in a future intervention.

C.1.6.2. Pantry Staff Measures

Food pantry staff will answer feasibility items for each of the intervention groups, such as desire to implement each food distribution strategy in the future, perceived appropriateness of the intervention given their organizational goals, perceived sustainability, and financial/staff resources needed to carry out the intervention longer term³². Staff participants will also respond to qualitative open-ended response items such as "Describe any challenges experienced with distributing ingredient bundles" "Describe any challenges experienced with distributing no prep ready-to-eat meals". Responses to the questionnaire will be followed with 30-minute semi-structured 1-1 interviews with study personnel, which give pantry staff the opportunity to directly voice any challenges or preferences that come up when implementing either approach. The pantry personnel perspective will allow us to design a feasible and sustainable longer-term intervention.

C.1.7. Analytic Plan

C.1.7.1. Analytic Plan for Pantry Client Data

Descriptive statistics (e.g., means, percentages, chi-squared tests of independence) will be used to describe participant characteristics and baseline differences. The independent variable of interest will be randomized group assignment (e.g., no prep ready to-eat-meals vs. ingredient bundles). Spearman's correlation and/or repeated measures Analysis of Variance (ANOVA) will be used to describe the association between group assignment and client's perceived diet quality at follow-up. If normally distributed, repeated-measures ANOVA is acceptable and will be used. If non-normal, Spearman's correlation will be used. For the other three outcomes of interest (satisfaction, acceptability, and liking) sum scores will be calculated, and model assumptions will be tested (e.g. residual distributions) before proceeding with repeated-measures Analysis of Variance (ANOVA) to test for group effects on study outcomes of interest and group-by-time interactions.

C.1.7.2 Analytic Plan for Pantry Staff Data

Descriptive statistics (e.g., means, percentages) will be used to describe quantitative items on staff feasibility and satisfaction. Qualitative thematic analysis of open-ended questionnaires and interviews will be synthesized into key findings and suggestions for future intervention development.

Form A

IRB # **STU 2022-0809**

4.b. List of the study intervention(s) being tested or evaluated under this protocol

 N/A - this study does not test or evaluate an intervention. Skip to item 4.d.			
#	Study intervention(s) being tested or evaluated under the protocol Add or delete rows as needed	Affiliate	Local Standard Practice? Indicate whether the intervention is considered acceptable practice locally for applicable institutions
1	
Figure 1. Example no prep ready-to-eat meals
  
Image Citation: https://www.supermarketnews.com/deli/spartannash-debuts-private-label-ready-made-meals
	 UTSW  PHHS  CMC  THR  TSRH  Other: Crossroads Community Services (Food pantry)	 Yes  Yes  Yes  Yes  Yes  Yes
2	
Figure 2. Example ingredient bundles or "meal kits"
  
Image Citation: https://www.everydayhealth.com/high-cholesterol/the-best-meal-kits-for-people-with-high-cholesterol/
	 UTSW  PHHS  CMC  THR  TSRH  Other: Crossroads Community Services (Food pantry)	 Yes  Yes  Yes  Yes  Yes  Yes

4.c. Risk:Benefit Analysis of study interventions being tested or evaluated under this protocol

For each study intervention identified in section 6b above, complete a risk:benefit analysis table.

(Two tables are provided, copy & paste additional tables as needed or delete both tables if this study does not test an intervention)

Form A

IRB #	STU 2022-0809
-------	---------------

4.c.

Study Intervention #1

No prep ready to eat meals

List each group exposed to this intervention on a separate line. (e.g., experimental, control, Arm A, Arm B, etc) Or state All Groups/Subjects	For each group, list the benefits of this intervention. (Benefits can be directly from the intervention or from a monitoring procedure likely to contribute to the subject's wellbeing). If there are no benefits, state "none".
Experimental	Participants, many of whom are food insecure, receive extra free food as a part of this study

If you are requesting a Waiver of Informed Consent, complete the table below.

If you have a consent form, list the reasonably foreseeable **risks** in the consent form (and do not complete this section).

List the risks according to the probability (likely, less likely or rare) and magnitude (serious or not serious).

(include: 1) expected adverse events; 2) rare and serious adverse events; 3) all other psychological, social, legal harms)

Do not delete frequency. Frequency must be estimated because it will assist you with determining which adverse events will require prompt reporting.

	Not serious	Serious
Likely These risks are expected to occur in more than 20 out of 100 subjects.	
 Not applicable 	
 Not applicable
Less likely These risks are expected to occur in 5-20 subjects or less out of 100 subjects.	
 Potential discomfort from answering personal questions or trying new study foods 	
 Not applicable
Rare These risks are expected to occur in less than 5 subjects out of 100		
 Not applicable

Form A

IRB #	STU 2022-0809
-------	---------------

4.c.

Study Intervention #2

Ingredient bundles or "meal kits"

List each group exposed to this intervention on a separate line. (e.g., experimental, control, Arm A, Arm B, etc) Or state All Groups/Subjects	For each group, list the benefits of this intervention. (Benefits can be directly from the intervention or from a monitoring procedure likely to contribute to the subject's well being). If there are no benefits, state "none".
Control	Participants, many of whom are food insecure, receive extra free food as a part of this study

If you are requesting a Waiver of Informed Consent, complete the table below.

If you have a consent form, list the reasonably foreseeable **risks** in the consent form (and do not complete this section).

List the risks according to the probability (likely, less likely or rare) and magnitude (serious or not serious).

(include: 1) expected adverse events; 2) rare and serious adverse events; 3) all other psychological, social, legal harms)

Do not delete frequency. Frequency must be estimated because it will assist you with determining which adverse events will require prompt reporting.

	Not serious	Serious
Likely These risks are expected to occur in more than 20 out of 100 subjects.	
 Not applicable 	
 Not applicable
Less likely These risks are expected to occur in 5-20 subjects or less out of 100 subjects.	
 Potential discomfort with answering personal questions or trying new study foods 	
 Not applicable
Rare These risks are expected to occur in less than 5 subjects out of 100		
 Not applicable

Form A

IRB #	STU 2022-0809
-------	---------------

		
4.d. List ALL other research procedures or components not listed in table 4.b. The combination of Tables 4b and 4d should account for all of the research procedures that will take place during this study.
 
Consider grouping similar procedures under a single component (e.g., blood work, CT = safety assessments)
		
#	Research component 
 individual procedures 
example: Eligibility Assessments
 
 History and physical Questionnaire Laboratory tests 
Add or delete rows as needed
	Column A Local Standard Practice Indicate the number of times each procedure will be performed as stipulated in the research plan that would be performed if the participant were not participating in the study.	Column B Research Only Indicate the number of times each procedure will be performed solely for research purposes (meaning that the participant would not undergo the same number of procedures or would not undergo the procedure(s) at the same frequency if they were not participating in the study)	Column D Risks If you are requesting a Waiver of Informed Consent, complete the table below. List the reasonably expected risks for each procedure or group of procedures under the following categories as appropriate: 
 • Serious and likely; • Serious and less likely; • Serious and rare; • Not serious and likely; • Not serious and less likely
1	Eligibility Assessment			
2	Questionnaires			
3	Selection of preferred no prep ready to eat meals OR ingredient bundles depending on group assignment			
4	Participants eat study meals			
	Participants eat the meals they selected	As frequently or infrequently as they like	Ideally once per day, but it's up to the client	Not serious and less likely – see 3D

Form A

IRB #	STU 2022-0809
--------------	----------------------

5	Participants receive reminders			
	Participants receive reminder calls, texts, and/or emails to try the study foods and come back for to their follow-up appointment	Clients receive reminder texts, calls, and/or phone calls if they have a scheduled appointment with the pantry, it varies depending on the client	Three times	Not serious and less likely – client's will confirm it's okay to contact them and indicate to us which is their preferred method of contact (call, phone, email)

5. Safety Precautions. (Describe safeguards to address the serious risks listed above.)

a. Describe the procedures for protecting against or minimizing any potential risks for each of the more than minimal risk research procedures listed above.
Not applicable, this study has no more than minimal risk
b. Where appropriate, discuss provisions for ensuring necessary medical or professional intervention in the event of adverse events, or unanticipated problems involving subjects.
Not applicable, this study has no more than minimal risk
c. Will the safeguards be different between/among groups?
 Yes  No
Not applicable

REFERENCES

- Participation Among Clients of a Nonprofit Food Distribution Site. *Clin Transl Sci*. Oct 2015;8(5):584-90. doi:10.1111/cts.12325

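### The planned group effect averages Day 0 and Day 15, so with comparable baselines it estimates half the Day 15 difference; no test is named as decisive, and the baseline pictures are not fixed by arm

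*Combined protocol and SAP*

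**What the plan says.** Order of events: Table 1 lists the Day 0 steps after consent as "2. Randomization 3. Questionnaires (demographics, current pantry use, acceptability, satisfaction, liking, diet quality", with selection of study foods as the next step. The narrative in C.1.5 agrees: randomisation follows consent, and then "Participants will complete questionnaires and then select meals".

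Awareness: C.1.5 states that "Participants will be unaware of their assignment until they are asked to select study meals".

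Pictures: in C.1.6.1, "Liking of study foods will be measured by showing the name and picture of the meal or ingredient bundle", on a nine-point scale. For the other picture-based outcome, "Acceptability will be measured by showing the name and picture of the meal"; its items ask whether the household ate the meal in the past two weeks and "whether they would select the meal again if given the opportunity in the future". The same liking and acceptability ratings are repeated at follow-up. No section says whether a client is shown the assigned format, both formats or one common set. C.1.5.2 adds that the ready-to-eat meals will be "selected based on the ability to closely replicate the meal as an ingredient bundle", so the dishes are meant to match across arms.

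Analysis: C.1.6.1 says the measures will show "differences at baseline as well as within- and between-group changes in acceptability, satisfaction, liking, and diet-quality after consuming meals over time". C.1.7.1 plans sum scores for satisfaction, acceptability and liking, and a repeated-measures ANOVA testing group effects and group-by-time interactions. It ranks neither test above the other. Only perceived diet quality, which has its own sentence, is tied to follow-up. Aim 1 predicts higher scores for ready-to-eat meals and names no time point.

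**The concern.** Day 15 is the only rating made after clients have had the study food, so it is the rating that bears on Aim 1. Under the plan, that difference is tested through one term that dilutes it with Day 0 and another that subtracts Day 0. The two terms answer different questions and can disagree, and the plan does not say which one decides.

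The Day 0 rating matters to both terms, and its meaning depends on the pictures. If all clients rate the same pictures without knowing their arm, Day 0 is an ordinary baseline. If each arm rates its own format after randomisation, Day 0 liking is already a response to the assignment. The questionnaire may then tell clients their arm before meal selection, contrary to C.1.5.

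Aim 1 is meant to establish which strategy clients prefer and to shape a later randomised trial, so the choice of test can change what is carried forward.

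**Working it through.** **Inputs.** From the documents: 35 clients per arm (section 3), two time points (Table 1) and the ANOVA terms (C.1.7.1). The plan gives no effect size, SD, significance level or correlation, so there is no stated calculation to reproduce. Assumed: SD 1 at each time, two-sided 5%, no dropout, and correlation r between Day 0 and Day 15 of 0.5 (range 0.3 to 0.7).

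**What each test estimates.** Let D0 and D15 be the differences between arms (ready-to-eat minus bundles) at the two visits.

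- Group main effect: (D0 + D15)/2, SE = √[(2/35)(1 + r)/2]
- Group-by-time interaction: D15 − D0, SE = √[(2/35) × 2(1 − r)]
- Day 15 comparison, unadjusted: D15, SE = √(2/35) = 0.239
- Day 15 comparison, baseline-adjusted: D15 − r × D0, SE = √[(2/35)(1 − r²)]

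The first line needs no assumed values. The main effect equals D15 only when D0 happens to equal D15.

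**Case 1: comparable baseline.** This covers satisfaction, and also liking and acceptability if all clients see the same pictures. The expected D0 is 0. Take D15 = 0.6 SD. Power is from the noncentral t with 68 degrees of freedom (67 when adjusted).

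| Test | Estimates | SE at r = 0.5 | Power at r = 0.5 | Power at r = 0.3; 0.7 |
|---|---|---|---|---|
| Main effect | 0.30 | 0.207 | 0.30 | 0.34; 0.27 |
| Interaction | 0.60 | 0.239 | 0.70 | 0.55; 0.89 |
| Day 15, unadjusted | 0.60 | 0.239 | 0.70 | 0.70; 0.70 |
| Day 15, adjusted | 0.60 | 0.207 | about 0.81 | 0.74; 0.93 |

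In simulation at r = 0.5, exactly one of the two planned tests is significant in 58% of trials. In about 49 of those 58 points it is the interaction alone.

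**Case 2: each arm rates its own format.** D0 is now a picture difference and need not be 0.

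- *No Day 15 difference; pictures favour ready-to-eat meals by an assumed 0.5 SD.* The main effect estimates (0.5 + 0)/2 = 0.25 and favours ready-to-eat meals in about 22% of trials (25% at r = 0.3, 20% at r = 0.7). The interaction estimates 0 − 0.5 = −0.5 and favours bundles in about 54% (41% to 76%). Both happen in the same trial in about 12% (10% to 15%). The unadjusted Day 15 test stays at 5%.
- *Day 15 difference 0.6 SD; same picture difference; r = 0.5.* The main effect estimates 0.55 with power 0.75. The interaction estimates 0.10 with power 0.07. The unadjusted Day 15 test keeps 0.70. Adjusting for the arm-specific rating estimates 0.6 − 0.5 × 0.5 = 0.35, with power of about 0.37.
- *Pictures favouring bundles by 0.25 SD; Day 15 difference 0.6 SD; r = 0.5.* The distortion reverses: the interaction estimates 0.85 and its power rises to 0.94.

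**The case against.** The strongest reply is that the plan already contains a usable test. With common pictures, the interaction estimates the Day 15 difference. It has the same power as an unadjusted Day 15 comparison at r = 0.5 and more at r = 0.7 (0.89 against 0.70). C.1.6.1 speaks of changes over time, which fits that term. This stands. A reader might infer that the plan has no valid test, or that the 58% disagreement makes the verdict arbitrary; neither follows, because most of that disagreement is the valid test detecting the difference. What remains is that C.1.7.1 does not make the interaction decisive, and that a baseline-adjusted comparison of data already being collected is more powerful at every correlation tried.

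A reader might also infer that randomising before baseline is an error in itself, or that clients will be unmasked. The documents do not support either. C.1.5 says clients are unaware until selection, and the matched dishes and the acceptability wording are compatible with one common set of pictures. Arm-specific pictures are only one reading of an open sentence. The figures in Case 2 also need an assumed picture difference, whose size and direction are unknown.

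Finally, this is a pilot, and the Day 15 contrast could be recovered from the planned model as the group effect plus half the interaction. That makes the change cheap; it does not tell the analyst which result answers Aim 1.

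**Conclusion.** The concern holds in two parts.

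First, for satisfaction, acceptability and liking, the plan leaves open which of two tests decides. With comparable baselines, the group main effect estimates exactly half the Day 15 difference. That is algebra and rests on no assumed value. The loss of power (0.30, against 0.70 for the interaction and about 0.81 adjusted) rests on the assumed 0.6 SD, the 5% level and the correlation. It would be too strong to say that the main effect misses most of the difference: it halves it, and under these inputs fails to detect it in about 70% of trials.

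Second, the pictures shown at Day 0 are unspecified while randomisation comes first. This is harmful only if each arm sees its own format. In that case Day 0 liking is no longer a baseline, both planned tests carry on-sight preference, and the questionnaire conflicts with C.1.5. Acceptability is affected only if its pictures also differ by arm. Satisfaction is at risk only if it is answered after such pictures, and no item order is fixed.

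This should be settled before enrolment, but it does not invalidate the design.

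**What to change.** 1. **Order.** Within the Day 0 visit, complete the baseline questionnaires before randomisation. If any picture ratings must be arm-specific, move all other items ahead of randomisation.
2. **Pictures.** State which pictures each client rates at Day 0 and at Day 15, and reconcile C.1.5 with C.1.6.1. If clients rate both formats, score the formats separately and do not pool them in one sum.
3. **Main test.** Name the Day 15 difference between arms as the main test for all three scores, with group-by-time as secondary. Adjust for the baseline score for satisfaction. Adjust for it for liking and acceptability only when the baseline pictures are the same in both arms. If they are arm-specific, label the Day 0 rating as expected liking and do not adjust for it.
4. **Acceptability.** Keep the planned sum score, or state explicitly that the item on selecting the meal again is analysed instead.

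**Cost.** Small edits to Table 1, C.1.5, C.1.6.1 and C.1.7.1; no added participants or visits. Showing both formats to everyone would lengthen the questionnaire and let clients see the format they do not receive. An unadjusted Day 15 test, needed only with arm-specific pictures, can have less power than the main effect when a large picture difference runs in the same direction: 0.70 against 0.80 to 0.69 at 0.5 SD, for correlations of 0.3 to 0.7.
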